# 9.4.2 Safety Endpoints

Safety and tolerability of MK-1654 in this study will be assessed by clinical review of all relevant parameters including AEs and laboratory values. The endpoints that will be used to assess the safety and tolerability of MK-1654 include the following:

- Number of participants experiencing solicited injection-site AEs (redness/erythema, swelling, and pain/tenderness) from Days 1 through 5 postdose
- Number of participants experiencing solicited daily body temperature, with fever defined as rectal temperature ≥102.2°F (≥39.0°C) or axillary temperature ≥101.7°F (≥38.7°C), from Days 1 through 5 postdose
- Number of participants experiencing solicited systemic AEs (irritability, drowsiness, and appetite lost) from Days 1 through 5 postdose
- Number of participants with anaphylaxis/hypersensitivity AESI from Days 1 through 42 postdose

- Number of participants with rash AESI from Days 1 through 42 postdose
- Number of participants experiencing nonserious AEs occurring from Days 1 through 42 postdose
- Number of participants experiencing SAEs through the duration of study participation (from the time the consent form is signed through completion of the participant's participation in the study; for complete details on SAE data collection, see Section 10.3.5).

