### **Tier 3 Events**

Safety endpoints that are not Tier 1 or 2 events are considered Tier 3 events. Only point estimates by treatment group are provided for Tier 3 safety parameters.

Table 7 Analysis Strategy for Safety Parameters

Safety Tier	Safety Endpoint	95% CI for Comparison of MK-1654 and Placebo	Descriptive Statistics
Tier 2	Any AE a	X	X
	Any Serious AE	X	X
	Any Drug-related AE	X	X
	Any Serious and Drug-related AE	X	X
	Discontinuation due to AE	X	X
	Solicited Injection-site AEs Days 1-5 Postdose	X	X
	Solicited Daily Body Temperature Days 1-5 Postdose	Х	X
	Solicited Systemic AEs Days 1-5 Postdose	X	X
	Anaphylaxis/hypersensitivity AESI Days 1-42 Postdose	Х	X
	Rash AESI Days 1-42 Postdose	X	X
	Nonserious AEs Days 1-42 Postdose	X	X
	AEs by SOC (incidence ≥1% of participants in 1 of the treatment groups)	Х	X
Tier 3	AEs by SOC (incidence <1% of participants in all of the treatment groups)		X

AE=adverse event; AESI=adverse event(s) of special interest; SAE=serious adverse event; CI=confidence interval; SOC=System Organ Class; X=results will be provided.

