#### **Assessment of severity**

- An event is defined as "serious" when it meets at least 1 of the predefined outcomes as described in the definition of an SAE, not when it is rated as severe.
- The investigator will assess the severity for each AE, SAE, and AESI (and other reportable safety event) reported during the study. Severity will be graded according to an adaption of NCI CTCAE version 5.0 as applicable for pediatric assessments. Where necessary, the NCI CTCAE scale has been adapted to conform to AE assessment for infant participants. Once the assessment has been made, the severity grade should be recorded in the "overall toxicity grade" section of the AE eCRF.

PROTOCOL/AMENDMENT NO.: 004-05

The severity of solicited injection-site AEs, solicited systemic AEs, elevated temperature, and AESI will be assessed according to the grading criteria (for Grade 1 through Grade 4) provided in Table 13 through Table 17. Additional grading definitions for AEs are provided in the separate study document: Severity Grading for Adverse Events.

- The severity for all other types of AEs that are not in the adapted NCI CTCAE will be determined by the investigator based upon clinical judgment and by using the following severity grading criteria (for Grade 1 through Grade 4):
  - **Grade 1**: Mild; mild symptoms; clinical or diagnostic observations only; intervention not indicated; awareness of symptoms, but easily tolerated.
  - Grade 2: Moderate; minimal, local, or noninvasive intervention indicated. Infant is definitely acting like something is wrong.
  - **Grade 3**: Severe or medically significant but not immediately life-threatening; intensive intervention indicated; disabling. Infant is extremely irritable or unable to do usual activities.
  - **Grade 4**: Life-threatening consequences; urgent intervention indicated.
  - Any AE that results in death will be assigned a severity grade of Grade 5.

It is important to distinguish between seriousness criteria and severity of an AE. Severity is a measure of intensity whereas seriousness is defined by the criteria in Section 10.3.3. A Grade 3 AE is not necessarily considered an SAE. For example, a Grade 3 headache that persists for several hours may not meet the definition of an SAE and would be considered a nonserious event, whereas a Grade 2 seizure resulting in a hospital admission would be considered an SAE.

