## Grading Scales for the Assessment of Severity for Solicited Injection-Site AEs, Solicited Systemic AEs, Elevated Temperature, and AESI

**Note:** Injection-site redness/erythema and injection-site swelling reported from Days 1 through 5 postdose will be evaluated by maximum size.

PRODUCT: MK-1654

PROTOCOL/AMENDMENT NO.: 004-05

 Table 13
 Solicited Injection-site AE Severity Grading Scale

Solicited Injection-	Severity Grade					
Site AE a	Grade 1	Grade 2	Grade 3	Grade 4		
Pain/Tenderness	Mild pain or tenderness with or without associated symptoms; does not interfere with normal activity	Moderate pain or tenderness. Interferes with normal activity	Severe pain or tenderness; prevents normal activity	Life-threatening consequences; urgent intervention indicated		
Erythema/Redness	Size measured as >0 and ≤1	Size measured as >1 and ≤2	Size measured as >2	Necrosis or exfoliative dermatitis OR results in ER visit or hospitalization		
Swelling	Size measured as >0 and ≤1	Size measured as >1 and ≤2	Size measured as >2	Necrosis or exfoliative dermatitis OR results in ER visit or hospitalization		

AE=adverse event; eDiary=electronic diary; ER=emergency room.

Table 14 Solicited Systemic AE Severity Grading Scale

Solicited	Severity Grade				
Systemic AE a	Grade 1	Grade 2	Grade 3	Grade 4	
Irritability	Mild; mild symptoms; clinical or diagnostic observations only; intervention not indicated; awareness of symptoms but easily tolerated.	Moderate; minimal local or noninvasive intervention indicated. Infant is definitely acting like something is wrong.	Severe or medically significant but not immediately life-threatening; hospitalization or prolongation of hospitalization indicated; disabling. Infant is extremely irritable or unable to do usual activities.	Life-threatening consequences; urgent intervention indicated.	
Drowsiness	Mild; asymptomatic or mild symptoms; clinical or diagnostic observations only; intervention not indicated; awareness of symptoms but easily tolerated.	Moderate; minimal local or noninvasive intervention indicated. Infant is definitely acting like something is wrong.	Severe or medically significant but not immediately life-threatening; hospitalization or prolongation of hospitalization indicated; disabling. Infant is extremely distressed or unable to do usual activities.	Life-threatening consequences; urgent intervention indicated.	

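### Severity grades are collected for solicited AEs and AESI, but no safety endpoint or Table 7 row uses them, so severe nonserious reactions and shifts from mild to severe get no planned between-group comparison

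*Combined protocol and SAP*

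**What the plan says.** **Collection.** Section 10.3.5 (Assessment of severity) has the investigator grade the solicited reactions, raised temperatures and AESI: their severity "will be assessed according to the grading criteria (for Grade 1 through Grade 4) provided in Table 13 through Table 17". Not every AESI term uses all four grades. In Tables 16 and 17, anaphylaxis, AGEP, DRESS and Stevens-Johnson syndrome start at Grade 3, and toxic epidermal necrolysis exists only at Grade 4. Dysphonia, drug eruption and urticaria stop at Grade 3. Grade 3 or 4 also has consequences during the study: an extra ADA sample for anaphylaxis/hypersensitivity AESI (Section 8.4.8.1) and a dermatology consultation for rash AESI (Section 8.4.8.2.2).

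**Analysis.** The endpoints in Section 9.4.2 are participant counts without grade. For local reactions the endpoint is "Number of participants experiencing solicited injection-site AEs (redness/erythema, swelling, and pain/tenderness) from Days 1 through 5 postdose". The rash endpoint has the same form: "Number of participants with rash AESI from Days 1 through 42 postdose". Table 7 in Section 9.6.2 follows this pattern with rows such as "Solicited Injection-site AEs Days 1-5 Postdose", and none of its rows is defined by grade. Under Section 9.6.2, an event gets a between-group 95% CI if at least 1% of a group has it or if Table 7 lists it. All other events get point estimates by group only.

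**Partial exceptions.** Fever is counted from 39.0°C rectal, the lower limit of Grade 2 in Table 15. Section 9.6.2 also summarizes maximum temperature by Brighton Collaboration cutoffs. Table 7 has rows for any serious AE and for any serious and drug-related AE.

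**The concern.** Safety and tolerability is a primary objective in healthy infants, and Section 9.9.1.1 says the sample size was chosen to give adequate safety information. A tolerability comparison should therefore show whether reactions are worse with MK-1654, as well as whether they are more frequent.

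Any-grade rows answer only the second question. The lowest grade for redness and swelling is "Size measured as >0 and ≤1", so any measurable mark counts. Irritability, drowsiness and appetite lost are non-specific in infants. If mild events make up most of a row, a small group of severe ones moves it very little. If the drug turns reactions that would have been mild into severe ones, the row does not move at all. The AESI rows pool terms that exist only at Grade 3 or above with terms gradable from Grade 1, such as wheezing and urticaria.

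The other rows only partly compensate. Section 10.3.5 states that "A Grade 3 AE is not necessarily considered an SAE", so the serious-AE rows miss severe nonserious reactions. The row for discontinuation due to AE says little about tolerability in a single-dose study, where Section 7.1 notes that study intervention cannot be discontinued once given.

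**Working it through.** **Inputs.** Group sizes are n1 = 2200 (MK-1654) and n0 = 1100 (placebo), at a 2-sided 5% level, all from Section 9.9.2. That section labels its incidences hypothetical and gives none by grade, so every event rate below other than the Table 9 pairs is an assumption, shown as a range.

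**Formula.** With placebo rate p0, MK-1654 rate p1 and d = p1 − p0:
- pooled rate pb = (1100·p0 + 2200·p1)/3300
- s0 = √[pb(1 − pb)(1/1100 + 1/2200)]
- s1 = √[p0(1 − p0)/1100 + p1(1 − p1)/2200]
- detection probability = Φ[(d − 1.96·s0)/s1] + Φ[(−d − 1.96·s0)/s1]

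The Farrington-Manning method cited for Table 9 reduces to this when the null difference is zero.

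**Step 1: reproduce Table 9.** The seven pairs, from 0.1 vs 0.8% to 30.0 vs 34.9%, give 77.0, 81.5, 78.9, 78.9, 79.9, 79.8 and 80.8%. This agrees with the stated approximate 80%. The first is lowest because the exact 80% difference is 0.74 points, printed as 0.7.

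**Step 2: compare Grade 3 or higher directly, 1.0-point excess.** For p0 = 0.5% and p1 = 1.5%: pb = 0.01167, s0 = 0.003965, s1 = 0.003352. Then (0.010 − 0.007772)/0.003352 = 0.665, which gives 74.7%.

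**Step 3: view the same excess through an any-grade row.** This assumes the extra infants would otherwise have had no event. For p0 = 20% and p1 = 21%: s0 = 0.014952, s1 = 0.014861. The two terms are Φ(−1.299) = 0.097 and Φ(−2.645) = 0.004, which total 10.1%.

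| Comparison, 1.0-point excess | Placebo rate | Detection probability |
|---|---|---|
| Grade 3 or higher, direct | 0.1% | 93.6% |
| | 0.3% | 84.1% |
| | 0.5% | 74.7% |
| Any-grade row | 2% | 38.3% |
| | 5% | 20.9% |
| | 10% | 13.8% |
| | 20% | 10.1% |
| | 30% | 9.0% |
| | 40% | 8.5% |

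For a 0.7-point excess, direct comparison gives 77.0, 60.1 and 49.0% at placebo rates of 0.1, 0.3 and 0.5%. The any-grade row gives 22% at a 2% placebo rate and 6.7-7.5% at 40-20%.

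**Step 4: a pure shift in grade.** If every extra severe reaction would otherwise have been a mild one, then p1 = p0 in the any-grade row and d = 0, whatever the sample size.

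**Step 5: the planned interval.** Take Table 9's first pair as Grade 3 or higher rates: 0.8% of 2200 is about 18 infants and 0.1% of 1100 about 1. The Miettinen-Nurminen 95% CI for 18/2200 vs 1/1100 (difference 0.73 points) is 0.25 to 1.21. The matching excess of about 15 infants on a 30% any-grade rate gives 675/2200 vs 330/1100 (difference 0.68 points), with CI −2.68 to 3.97. The first interval excludes zero and the second does not. At 18/2200 = 0.82%, the severe category is also below the 1% threshold, so it would get an interval only if Table 7 listed it.

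**The case against.** **Severe events often reach the serious-AE rows.** Table 14 ties Grade 3 irritability, drowsiness and appetite lost partly to indicated hospitalization. Tables 16 and 17 do so for several AESI terms, and inpatient hospitalization makes an event serious (Section 10.3.3). This stands and narrows the point. It does not close it, because Grade 3 can also be met by an infant being unable to do usual activities, and Grade 3 injection-site redness or swelling depends on size alone.

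**The 1% rule is reasoned.** Section 9.6.2 argues that an interval on very few events may exclude zero without known clinical meaning. That caution is fair for unselected AE terms, but here the protocol has fixed the clinical meaning in advance through its grading scales. Listing a row in Table 7 is already the plan's route around the threshold. The rule is also not the main obstacle: of the six direct-comparison scenarios above, only 0.1% plus 0.7 points leaves MK-1654 below 1%.

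**The assumed rates drive the size.** This also stands. Masking is much weaker at low any-grade rates, which may apply to the AESI rows, and 40% lies outside Table 9's range. Section 9.6.2 treats Tier 2 intervals as descriptive, so the detection probabilities measure how informative a row is and are not the power of a planned test.

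**Nothing is lost.** Grades are on the eCRF, safety is judged by clinical review, every Table 7 row also gets descriptive statistics, and the eDMC sees treatment-level or participant-level data. The note in Section 10.3.5 that redness and swelling are evaluated by maximum size sits with the grading scales and does not define an analysis. A reader might infer that the supplemental SAP (sSAP) could not hold a by-grade analysis. Section 9 does not support that, because it also lets the sSAP document changes to nonconfirmatory analyses. The sections shown do not promise one there, however.

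**Conclusion.** The gap is real but narrower than it first looks. As written, the plan makes no between-group comparison by grade. It therefore cannot show a shift from mild to severe, and it is a weak instrument for a small excess of severe nonserious reactions. This mainly concerns solicited injection-site AEs, solicited systemic AEs and the two pooled AESI rows. For a 1.0-point excess, direct comparison detects it with 75-94% probability, against 38% at a 2% any-grade placebo rate, falling to 8.5% at 40%. These figures rest on assumed rates, on the full 2200 and 1100 infants being evaluable as in Section 9.9.2, and on the any-grade row receiving the whole excess.

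A reader might infer that severe reactions go wholly unseen. The documents do not support that: temperature is partly handled by level, and severe events that are serious are compared in the serious-AE rows. Nor do they support inferring that every AESI term is graded 1 to 4, or that an excess of severe reactions with MK-1654 is expected. This is an inexpensive improvement in pre-specification. It does not affect the efficacy conclusions.

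**What to change.** Keep the any-grade rows and add these to Table 7 as listed Tier 2 rows, so that the 1% threshold does not apply:
- Days 1 through 5: Grade 3 or higher solicited injection-site AE, solicited systemic AE, and elevated temperature.
- Days 1 through 42: Grade 3 or higher anaphylaxis/hypersensitivity AESI, and rash AESI.

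Count each infant once per row at the maximum grade. Give the Miettinen-Nurminen 95% CI already planned in Section 9.1, and label it descriptive and unadjusted, as Section 9.6.2 does for Tier 2. Add a summary by maximum grade and treatment group for the same categories. Make the change before unblinding, so that the severity cutoff is not chosen after seeing the data.

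The cost is SAP wording, five rows and one summary table, all from data already collected. No new data, alpha or sample size is needed. The downside is a few more unadjusted intervals, some on very small counts, which need the same caution that Section 9.6.2 already gives.

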# 9.6.3 Demographic and Baseline Characteristics

The comparability of the treatment groups for each relevant demographic and baseline characteristic will be assessed by the use of tables and/or graphs. No statistical hypothesis tests will be performed on these characteristics. The number and percentage of participants

Indicates broad AE category of the number of participants reporting any AE.

screened and randomized and the primary reasons for screening failure and discontinuation will be displayed. Demographic variables (eg, age, gender, race, and ethnicity), baseline characteristics (including medical history as outlined in Section 8.1.4), primary and secondary diagnoses, and prior and concomitant therapies will be summarized by treatment group either by descriptive statistics or categorical tables.

# 9.6.3.1 Population Pharmacokinetic Analyses

Based on PK data obtained within this study, a separate population PK analysis will be performed and reported separately. The prospective details of this analysis will be specified in a separate population PK analysis plan.

# 9.7 Interim Analyses

A total of 2 IAs are planned for this study. All IAs will be conducted by an external unblinded statistician. Enrollment will not be paused during IAs/review of results by eDMC. All available safety, PK, and RSV disease incidence data will be summarized for each IA. Ongoing PK bioanalysis and PK modeling will be conducted by a separate, unblinded modeling group and external bioanalysts. In addition to these planned IAs, the eDMC will review available safety and RSV disease incidence data from this study at least once every 6 months while the study is still enrolling or as outlined in the eDMC charter.

Treatment-level results and/or participant-level data from the IA will be provided by the unblinded statistician to the eDMC. The extent to which individuals are unblinded with respect to results of the IAs will be documented by the unblinded statistician. The results of the IAs will not be shared with the investigators prior to the completion of the study. Participant-level unblinding will be restricted to the external unblinded statistician and scientific programmer performing the IA, who will have no other responsibilities associated with the study.

IA#1: After the last participant randomized in the Phase 2b cohort completes the Day 42 visit and the safety data are available, the first IA will be conducted. Summaries of the safety data will be reviewed by the eDMC. Additionally, the eDMC will review a summary of the available PK data, and estimates of efficacy along with the 95% CIs for the endpoints of RSV-associated MALRI and RSV-associated hospitalization (based on the exact binomial method proposed by Chan and Bohidar [Chan, I. S. F. and Bohidar, N. R. 1998]). Futility of the primary efficacy endpoint will not be assessed at this IA. The eDMC will assess the benefit versus risk for continued enrollment and a recommendation on whether the study should continue will be made by the eDMC. The study will not stop for success of the primary efficacy hypothesis at the IA. If the study stops at the IA, no further participants will be enrolled. However, participants that have already been enrolled in the study will continue to be monitored for safety for 365 days postdose.

IA#2: If the study continues, the second IA for futility evaluation will be conducted when 40 total RSV-MALRI cases in the combined MK-1654 and placebo groups have been observed in the study. If  $\geq$ 21 cases are observed in the MK-1654 group (observed efficacy <50%), the study may stop for futility. If the study stops at this IA due to futility, no further

participants will be enrolled. However, participants that have already been enrolled in the study will continue to be monitored for safety for 365 days postdose. The study will not stop for success of the primary efficacy hypothesis at the IA. The operating characteristics of the futility criterion are shown in Table 8. Summaries of the available safety and PK data will be summarized and reviewed at the second IA.

Table 8	Futility Evaluation	Operating	Characteristics (	(Interim Analysis #2)	

Analysis Time Point	Total Cases to Accrue	Stop for Futility (MK-1654 Cases)	Observed Efficacy (%) (95% CI)	True Efficacy	Probability of Stopping for Futility at IA#2 (%) a	Probability of NOT Stopping for Futility at IA#2 (%) a,b
IA 2	40	≥21	45 (-9, 72)	25% (Null)	87.0	13.0
				50%	43.7	56.3
				60%	19.3	80.7
				70%	3.8	96.2
				80%	0.1	99.9
				90%	0.0	100.0

CI=confidence interval; IA=interim analysis.

If the study does not stop at the second IA, the study will continue as planned. After all participants in the global study (see Appendix 7 regarding enrollment in China) have completed 180 days postdose follow-up, a database lock will be executed, and the Sponsor study team will be unblinded. All analyses to evaluate the primary, secondary, and tertiary objectives of the study will be conducted, and a CSR will be written. A separate blinded Sponsor study team will be appointed to conduct the remainder of the study. All participants will continue in the study until all follow-up assessments per the protocol have occurred. When all participants have completed all follow-up assessments per the protocol 365 days postdose, a database lock will be executed, and the supplemental CSR will be written. If the first 1650 participants enrolled finish the follow-up through RSV Season 2 by the time all participants finish the follow-up through 365 days postdose, all analyses will be written in 1 supplemental CSR; otherwise, another supplemental CSR will be written at the end of RSV Season 2 follow-up. Investigators, study participants, and their legally accepted representatives will remain blinded to individual treatment assignments throughout the duration of the entire study and will be unblinded upon completion of the end-of-study CSR.

The details for the reports of data reviewed by the eDMC and processes by which recommendations and decisions are reached and communicated by the eDMC will be documented in the eDMC charter for the Sponsor. The eDMC charter will be referenced in the CSR. Prior to final study unblinding, Sponsor individuals who have been unblinded at any level will not be involved in any discussions regarding modifications to the protocol,

<sup>a Probability is based on the exact binomial method proposed by Chan and Bohidar [Chan, I. S. F. and Bohidar, N. R. 1998].

b =100 – probability of stopping for futility at IA#2.

statistical methods, identification of protocol deviations, or data validation efforts after the IAs.

## 9.8 Multiplicity

The overall 1-sided Type 1 error in testing the efficacy hypotheses is controlled at 2.5% based on a gatekeeping procedure.

The primary efficacy hypothesis will be tested at an overall 1-sided Type 1 error equal to 2.5% (see Section 9.9.1.1). The secondary efficacy hypothesis regarding RSV hospitalization from Days 1 through 150 postdose will be tested at 1-sided Type 1 error of 2.5% only if the primary efficacy hypothesis is successfully demonstrated (see Section 9.9.1.2).

A futility analysis of the primary endpoint will be conducted when 40 total RSV-MALRI cases in the combined MK-1654 and placebo groups have been observed. No Type 1 error adjustment is needed for the futility analysis because there is no possibility to stop the study and conclude efficacy.

